## 5. Randomization

Random assignment was done by drawing lots from every four eligible ICU admissions each day.

## 6. Outcome Measures

- Primary: Change in SpO2 over six time points
- Secondary: Respiratory rate, arterial blood gas parameters (SaO2, PO2, PCO2, pH, Lactate, Sodium)

## 7. Statistical Methods

- Descriptive statistics: mean, standard deviation, frequency, and percentage
- Inferential statistics: Wilk's Lambda for repeated measures, paired t-tests, independent t-tests
- Effect size: Cohen's d
- Software: SPSS v22

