STUDY DOCUMENT

Official Study Title:

The Effect of Prone Position on Oxygen Saturation, Blood Gas Parameters, and Respiratory Rate in Intensive Care Patients with COVID-19-induced ARDS

NCT Number: NCTXXXXXXX

Document Type: Study Protocol

Document Date: 26 May 2025

STUDY PROTOCOL

1. Official Title

The Effect of Prone Position on Oxygen Saturation, Blood Gas Parameters, and Respiratory Rate in Intensive Care Patients with COVID-19-induced ARDS

2. Brief Title

Effect of Prone Position in COVID-19 ARDS Patients

3. Principal Investigator(s)

- [name], RN, Ph.D. – Diyarbakır Provincial Health Directorate
- [name]. [name], Ph.D. – Inonu University Faculty of Nursing

4. Study Sites

General and Intermediate Intensive Care Units, Eastern Turkey

5. Study Period

Start Date: April 1, 2021

End Date: August 30, 2021

6. Background and Rationale

ARDS is a common complication of severe COVID-19, associated with high mortality. Prone positioning has been shown to improve oxygenation and lung compliance in ARDS. This study investigates its short-term effectiveness in non-intubated patients.

7. Objectives

To evaluate the impact of a 30-minute prone position on:

- Oxygen saturation (SpO₂, SaO₂, PO₂)
- Respiratory rate
- Blood gas parameters (pH, PCO₂, Lactate, Sodium)

8. Study Design

Randomized controlled trial

Parallel group, repeated measures (6 total timepoints)

1:1 allocation (n = 90, 45 per group)

9. Eligibility Criteria

Inclusion Criteria:

- Age ≥ 40
- ICU hospitalization for COVID-19-induced ARDS
- Intubated and responsive to assessment

Exclusion Criteria:

- Sensory impairments (vision/hearing)

- Cognitive impairments
- Patients who died or no longer required ICU during study

10. Intervention

Experimental Group: 30 minutes prone position once daily for 2 days

Control Group: Supine standard care

11. Outcomes

Primary Outcome:

- Change in oxygen saturation (SpO_2) post-prone positioning

Secondary Outcomes:

- Respiratory rate
- Arterial blood gas values (SaO_2 , PO_2 , PCO_2 , pH, lactate, sodium)

12. Randomization

Simple randomization by drawing lots

Allocation ratio 1:1

13. Blinding

Open-label (no blinding)

14. Statistical Methods

Paired and independent t-tests

Wilk's Lambda

Cohen's d for effect size

SPSS used for data analysis

15. Ethical Considerations

Approval: Gazi Yasargil Training and Research Hospital Ethics Committee (15.01.2021 / No: 626)

Verbal and written consent obtained

Conducted per Declaration of Helsinki

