## 3. Study Design Summary

This is a randomized controlled trial with a parallel group and repeated measures over six time points.

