## 4. Sample Size Justification

A total of 90 patients (45 per group) were selected using 95% confidence level, 5% margin of error, and an effect size of 0.70.

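### Neither document says which test, contrast or reading decides the primary change in SpO2, and the listed paired t-tests cannot compare prone with supine

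*SAP*

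**What the plan says.** SAP 7 (Statistical Methods) gives the inferential analysis in one line: "Inferential statistics: Wilk's Lambda for repeated measures, paired t-tests, independent t-tests". Protocol 14 lists "Paired and independent t-tests" and Wilks' lambda, also with no further detail. No test is tied to an outcome, a contrast between arms, a reading or an order of use, and the factor tested by Wilks' lambda is not named. SAP 8 and 9 deal only with exclusions and completers, so they do not fill the gap.

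The design is described as "parallel group and repeated measures over six time points" in SAP 3 and as "Parallel group, repeated measures (6 total timepoints" in Protocol 8. There is a separate supine control group, and the intervention in Protocol 10 is "30 minutes prone position once daily for 2 days".

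SAP 6 words the primary outcome as "Primary: Change in SpO 2 over six time points". Protocol 11 words it as "Change in oxygen saturation (SpO_2) post-prone positioning". Neither document places the six readings before, during or after the two sessions.

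**The concern.** The trial's question is whether SpO2 changes more with prone positioning than with supine care. Only a between-arm comparison answers it. The list mixes methods that make that comparison with methods that do not, and gives none of them priority. Several analyses could therefore supply the headline result.

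Two things are at stake. First, the two eligible methods, Wilks group-by-time and an independent t-test, can reach different conclusions on the same data, so the conclusion may depend on which one is reported. Second, if a paired t-test or Wilks for time were reported as the result, a change common to both arms could be taken for a prone effect.

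The outcome wordings add to the uncertainty. One points towards a joint test of the whole profile, the other towards the reading or readings after a session.

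**Working it through.** **1. What each listed method compares**

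| Method | Compares prone with supine? | Left open |
|---|---|---|
| Independent t-test | Yes | Which reading; raw value or change |
| Wilks, group-by-time | Yes, all changes jointly | Whether this effect is meant |
| Wilks, time | No, change over time | Whether this effect is meant |
| Paired t-test | No, an arm with itself | Its role |

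**2. The plan's own figure.** SAP 4 gives 45 per group and "an effect size of 0.70", without power, sidedness or the test. The total of 90 therefore cannot be reproduced from the stated inputs alone. If 0.70 is the standardised between-arm difference at one reading, an independent t-test has noncentrality 0.70 × √(45/2) = 3.32. With 88 df and two-sided 5%, power is 90.7%. The sample size is compatible with one such test, but the SAP does not say that this test is primary.

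**3. Model for the illustrations.** From the documents: 45 per arm, six readings, effect size 0.70. Assumed, because the documents give no value: normal data with equal correlation ρ of 0.5, 0.7 or 0.9 between readings; first reading before the intervention; effect at one later reading only; an alternative effect of 0.4 SD; 45 analysed per arm; two-sided 5%.

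**4. Do the two eligible tests agree?** Both documents define the outcome as a change, so the t-test is on change from the first reading (88 df). Wilks group-by-time uses F(5, 84) on the five differences from the first reading. Share of simulated trials in which exactly one is significant (40,000 trials per cell):

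| Effect | ρ = 0.5 | ρ = 0.7 | ρ = 0.9 |
|---|---|---|---|
| None | 7% | 7% | 7% |
| 0.4 SD | 28% | 25% | 1.5% |
| 0.70 SD | 10% | 1.3% | 0% |

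**5. What unranked testing could produce under no prone effect.** The plan prescribes neither of these uses.

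- Counting any one of five change-from-baseline t-tests as success gives about 18% false positives. Under this model any two of the five changes have correlation 0.5 whatever ρ is, so the figure does not depend on ρ. Wilks group-by-time alone gives about 5%, and requiring it first cannot exceed that.
- Reading a significant rise in the prone arm with no significant change in control as an effect: let both arms share a drift of δ SDs of the change. Each paired t has 44 df and noncentrality δ√45. The probability is P(prone significantly up) × P(control not significant). At δ = 0.3 the noncentrality is 2.01, giving 0.503 × 0.497 = 25.0%. For δ = 0 to 0.6 in steps of 0.1 the results are 2.4, 8.6, 19.2, 25.0, 18.9, 8.5 and 2.4%.

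**6. Power of the candidate primary tests** (effect d at one reading, ρ = 0.5 / 0.7 / 0.9)

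- t-test on the raw reading, noncentrality d√22.5: 91% at 0.70 and 47% at 0.4, for every ρ.
- t-test on change, noncentrality d√22.5 / √(2(1 − ρ)): 91 / 99 / 100% at 0.70; 47 / 68 / 99% at 0.4.
- Wilks group-by-time, noncentrality 22.5 × d² × (5/6) / (1 − ρ), which at 0.70 is 18.4 / 30.6 / 91.9: power 91 / 99 / 100%; at 0.4, 41 / 64 / 99%.
- Contrast adjusted for the first reading, 87 df, noncentrality d√22.5 / √(1 − ρ²), which at 0.70 is 3.83 / 4.65 / 7.62: power 97 / above 99 / 100%; at 0.4, 58 / 75 / 99%.

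**The case against.** The strongest reply is that the plan has a natural reading: a repeated-measures trial with two arms, Wilks' lambda for group-by-time first, t-tests as follow-up. That sequence would control the global error and is built entirely from methods already listed. Calling paired t-tests inferential may do no more than separate them from the descriptive statistics. This is a fair reading, but it is not written down. If it was intended, stating it takes a sentence.

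Several stronger conclusions are tempting, and the documents do not support them:

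- *That no valid between-arm test is planned.* Independent t-tests are listed, and Wilks group-by-time is available under the listed name. What is missing is the assignment.
- *That the two outcome definitions contradict each other.* Protocol 8 also has six time points, so the wordings differ in precision only.
- *That the eligible tests often clash whatever the correlation.* At 0.4 SD a t-test on the raw reading disagrees with Wilks in 32%, 37% and 52% of trials as ρ rises. But both documents define a change, and at ρ = 0.9 nearly all of that gap is power lost by ignoring the first reading. On the change itself it is about 1.5%.
- *That the plan carries an 18% false-positive rate, or will treat a one-arm paired result as efficacy.* No section says so. Those figures describe possible misuse.
- *That the tests were chosen after seeing results.* A document date does not show when the choice was made.

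It also stands that 0.4 SD is an assumption, that the adjusted contrast appears in neither document, and that its power advantage vanishes at high correlation.

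**Conclusion.** The point holds as a gap in specification that must be closed: the primary conclusion has no stated decision rule, and the listed methods include some that cannot answer the between-arm question.

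The practical size depends on quantities that the documents do not give. Under the assumed model, the choice between the two eligible tests changes the verdict in about 7% of trials with no effect, in up to about 28% at 0.4 SD, and in 10% or fewer at the SAP's 0.70 if that is the between-arm difference at one reading. At correlation 0.9 the choice hardly matters once there is a real effect of either size. The 18% and the 2% to 25% in the working are conditional on decision rules that the plan does not adopt; they show why the rule should be stated, not what the trial's error rate is.

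**What to change.** In both documents:

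- Use one wording for the primary outcome and state when each of the six readings falls relative to the two sessions.
- Name one between-arm primary test. Preferably this is prone minus supine SpO2 at the stated post-session reading or readings, adjusted for pre-intervention SpO2, two-sided 5%, with a 95% CI. At 0.70 SD its power is about 97% or more, against 91% for a t-test on the raw reading and 91%, 99% and 100% for a t-test on change. Over the change score, the gain lies mainly at lower correlation.
- An acceptable alternative, using only methods already listed, is Wilks' lambda for group-by-time as primary, with independent t-tests only if it is significant.
- In either case, make paired t-tests descriptive, limit Wilks' lambda to group-by-time, and label other time-point and secondary-outcome p-values exploratory or adjust them.
- Disclose that the choice was fixed after data collection, unless an earlier plan exists: Protocol 5 ends the study on August 30, 2021, and both documents are dated 26 May 2025.

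The cost is wording in two documents, some reanalysis of SpO2 already collected and fewer confirmatory p-values. The adjusted contrast requires that one of the six readings precede the intervention, which a change outcome implies but neither document states. None of this restores prespecification.

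### The SAP names no deciding test and no multiplicity rule for SpO2 over six readings; if separate between-arm t-tests can each support a claim, the false-positive chance is roughly 7-25%, not 5%

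*SAP*

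**What the plan says.** SAP section 6 makes SpO2 the only primary measure and defines the outcome as its change "over six time points". No reading, contrast or summary is singled out. Protocol section 11 gives the primary outcome as the change in SpO2 after prone positioning, also without a time point.

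SAP section 7 lists the inferential methods in one line: "Wilk's Lambda for repeated measures, paired t-tests, independent t-tests". Protocol section 14 lists "Paired and independent t-tests" together with Wilks' Lambda. No method is assigned to an outcome, a reading or a comparison. The SAP does not say whether Wilks' Lambda is a group-by-time test or is applied within each arm.

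Neither document mentions a multiplicity adjustment, a testing order or a gate. Neither says which of the six readings come before and which after a prone session.

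**The concern.** Of the listed methods, only the independent t-test gives a between-arm SpO2 difference at a given reading. Wilks' Lambda gives one overall test and no such estimate. With six readings and no rule tying the tests together, an analyst who follows the list could compare the arms at several readings and report whichever is significant as an effect on the primary outcome.

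If prone positioning had no effect, the 5% level would then apply to each t-test separately and not to the conclusion drawn from the set. At stake is whether a positive SpO2 result carries the error rate that a reader will assume.

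**Working it through.** **Inputs from the documents.** 45 patients per arm (Protocol section 8, SAP section 4); six readings (Protocol section 8, SAP section 3); "95% confidence level, 5% margin of error, and an effect size of 0.70" (SAP section 4).

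**Inputs assumed.** Two-sided 5% per test (inferred from the 95% confidence level); effect size read as Cohen's d; two to six between-arm SpO2 tests; between-reading correlation 0.3-0.9; normal data; any significant reading counts as a positive finding.

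**Step 1: the plan's own figure.** Use n per arm = 2(z₁ + z₂)²/d² with d = 0.70, where z₁ is the significance quantile and z₂ the power quantile.
- One-sided 5%, 95% power: 2(1.645 + 1.645)²/0.49 = 44.2, so 45 per arm. The exact t calculation also gives 45.
- Two-sided 5%, 90% power: 2(1.960 + 1.282)²/0.49 = 42.9, so 43 (44 by exact t).

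The stated 45 per arm is reproduced once the missing power and sidedness are supplied, and in each case for a single test. With 45 per arm, one two-sided 5% test has 90.7% power at d = 0.70.

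**Step 2: upper reference for the error rate.** For k independent tests the chance of at least one false positive is 1 − 0.95^k. This gives 9.75% for k = 2 and 26.5% for k = 6. Readings on the same patient are correlated, which lowers these figures.

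**Step 3: correlated readings.** Simulation under no effect, 45 per arm, 40,000 trials per setting, equal correlation between readings. Chance that at least one t-test has p < 0.05:

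| Tests | corr. 0.3 | 0.5 | 0.7 | 0.9 |
|---|---|---|---|---|
| 2 | 9.1% | 8.9% | 8.4% | 7.0% |
| 3 | 13.6% | 12.6% | 10.8% | 8.2% |
| 4 | 17.5% | 15.3% | 13.2% | 9.8% |
| 5 | 21.0% | 18.6% | 15.1% | 10.1% |
| 6 | 24.5% | 20.7% | 16.4% | 11.0% |

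If correlation decays with the distance between readings, six tests give 25.0%, 23.8%, 20.1% and 13.8% at the same values. The overall range is therefore about 7-25%.

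**Step 4: tests of change.** Take the first reading as baseline and test the five changes from it. With equal correlation r, two such changes have covariance (1 − r)σ² and variance 2(1 − r)σ² each. Their correlation is 1/2 whatever r is, so the error rate should not depend on r. The simulation agrees: 18.1-18.7% for r from 0.3 to 0.9. With decaying correlation it is 17.5% to 15.0%.

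**Step 5: what Wilks' Lambda would do.**
- As the only test (group by time): 4.9-5.0% under no effect.
- As a gate before unadjusted t-tests, with no effect at any reading: 1-3% (correlation 0.9 to 0.5).
- As a gate, with a true d = 0.70 effect at one later reading and none at the other four: a false claim at one or more of those four in 14.9%, 14.6%, 13.2% and 9.5% of trials (correlation 0.3, 0.5, 0.7, 0.9). A real effect at one reading opens the gate, and the remaining tests are then unprotected.
- As an alternative to the t-tests, where either may count: 23.1%, 19.5% and 14.5% (correlation 0.5, 0.7, 0.9).

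**Step 6: effect of adjustment.** Testing five readings at 0.05/5 = 0.01, the first Holm step, brings the false-positive chance under no effect to 2.4-4.4%. Power for d = 0.70 at a single reading is then 75.2%, or 73.1% if the divisor is six. With d = 0.70 at all five later readings, the chance of at least one claim is 96.5% at correlation 0.5 and 86.1% at 0.9.

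**The case against.** A reader might infer that the plan does compare SpO2 between arms by t-test at all six readings, and so carries an error rate of 11-24% as a matter of fact. The documents do not support that.
- No sentence says that SpO2 is t-tested at each reading. The trial has eight outcomes (SpO2, respiratory rate and six blood gas values), so the plural could mean one t-test per outcome.
- Wilks' Lambda is the only method that the SAP ties to repeated measures, and the primary outcome is defined over the repeated readings. If the group-by-time test alone decides the primary outcome, the error is 5% and there is no family to adjust.
- The 11-24% range counts all six raw readings, although at least one is presumably taken before treatment and both documents define the outcome as a change.

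These points stand, and they are why the size is given conditionally and over a wider range. They do not close the gap. The SAP does not give Wilks' Lambda the deciding role, and every count from two to six per-reading tests exceeds 5%.

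It can also be argued that naming a primary test settles everything. That holds for the primary conclusion. It does not hold for claims about single readings, as the gate results show.

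**Conclusion.** The concern holds in conditional form. The text does not assure 5% control for the primary SpO2 outcome, because it names neither a deciding test nor a rule for several tests. If t-tests at separate readings may each support a claim, the false-positive chance is roughly 7-25%, and about 18% for five changes from the first reading under equal correlation. These figures rest on the assumed number of tests, correlation, two-sided 5% level and normality. The reading schedule, which would fix the number of tests, is not given.

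The size is not established for the analysis as actually carried out. It would be about 5% if a single overall between-arm test decides and no claims are made at individual readings. This should be corrected before results are reported. Confidence is medium, because the plan can be read in more than one way.

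**What to change.** Add to SAP section 7: *The primary SpO2 conclusion rests on one overall between-arm test (the Wilks' Lambda group-by-time test). Any between-arm SpO2 t-tests at the separate post-baseline readings form one family; their p-values are Holm-adjusted, and an effect at a reading is claimed only if the adjusted p-value is below 0.05. Unadjusted values are descriptive.*

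State which of the six readings are post-baseline, since this fixes the size of the family and keeps the baseline comparison from using up alpha. Label the rule as added after data collection: the study period ended on 30 August 2021 (Protocol section 5) and the SAP is dated 26 May 2025 (SAP section 10). It can govern reporting but cannot be presented as prespecified.

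The cost is a few sentences and a Holm step done by hand or spreadsheet on the SPSS output, with no new data. The downside is less favourable per-reading p-values. For d = 0.70 at one reading only, power falls from about 91% to about 75% with five readings in the family. The loss is smaller if the effect is present at several readings.

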## **10. Version History**

Version 1.0

Date Last Updated/Approved: 26 May 2025

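### The plan names no baseline covariate, SpO2 change contrast or primary test, and the only listed test that gives a between-arm difference is an unadjusted t-test, usually less precise than ANCOVA

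*SAP*

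**What the plan says.** SAP section 7 gives the inferential methods in one line: Wilks' Lambda, tagged "Lambda for repeated measures", followed by "paired t-tests, independent t-tests". Cohen's d is the effect size. Protocol section 14 agrees, with "Paired and independent t-tests" and Wilks' Lambda on separate lines. No covariate appears in either document.

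The primary outcome is worded as a change in both. SAP section 6 has "Primary: Change in SpO 2 over six time points"; protocol section 11 has "Change in oxygen saturation (SpO_2) post-prone positioning". Neither says when the six measurements are taken, which is the reference value, or which values are subtracted, averaged or compared between arms. No test is assigned to the primary outcome, and the SAP does not say whether Wilks' Lambda tests arm by time or time alone.

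The sample size (SAP section 4) is 45 per group, based on "an effect size of 0.70".

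**The concern.** A randomised comparison of SpO2 needs one between-arm estimate with an interval. Of the listed methods, the paired t-test works within an arm, and Wilks' Lambda is an overall test that returns a p-value and no difference. That leaves the independent t-test, on a variable the plan does not define. Since both documents speak of change, a change-score t-test is the likelier reading; a comparison of post values is possible but less likely.

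Neither version uses the first measurement efficiently. A change score subtracts it with a fixed weight of 1; a post-value comparison gives it weight 0. ANCOVA estimates the weight from the data. Apart from a small cost for estimating it, ANCOVA is therefore more precise than the change score unless the true slope is close to 1, and more precise than the post value unless the slope is close to 0. What is at stake is the width of the main SpO2 interval, and a choice of contrast that can still be made after the data are seen.

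**Working it through.** **The plan's own figure.** The total of 90 cannot be derived from SAP section 4 alone, because power and sidedness are not stated. Reading 0.70 as Cohen's d with alpha 0.05, a one-sided test with 95% power gives 90, and a two-sided t-test with 90% power gives 88. So 90 is not shown to be wrong. Two-sided power at 45 per arm is 90.7% by noncentral t.

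**Inputs.** From the documents: 45 per arm, d = 0.70. Assumed, because the documents are silent: correlation r between first and later SpO2 of 0.3, 0.5, 0.7 or 0.8; one later value; equal SDs, set to 1; a first value that is a true baseline.

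**Formulas.** The variance per patient entering the between-arm difference is:
- change score: 2(1 − r)
- post value: 1
- ANCOVA: 1 − r²

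SE excess over ANCOVA = √(variance ratio) − 1. The 95% CI half-width = t(0.975) × √(2 × variance / 45), with 88 df for the t-tests and 87 for ANCOVA.

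| r | Change variance | ANCOVA variance | Change-score SE excess | Post-value SE excess | Half-width, change (SD) | Half-width, ANCOVA (SD) |
|---|---|---|---|---|---|---|
| 0.3 | 1.40 | 0.91 | 24% | 5% | 0.50 | 0.40 |
| 0.5 | 1.00 | 0.75 | 15% | 15% | 0.42 | 0.36 |
| 0.7 | 0.60 | 0.51 | 8% | 40% | 0.32 | 0.30 |
| 0.8 | 0.40 | 0.36 | 5% | 67% | 0.26 | 0.25 |

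Example at r = 0.3: √(1.40/0.91) − 1 = 0.240. The post-value half-width is 0.42 SD at every r. Allowing for chance baseline imbalance (ANCOVA variance times 1 + 1/86) lowers the excesses by about one percentage point or less.

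**Unequal SDs.** Let k be baseline SD divided by post SD. The change-score variance is 1 + k² − 2rk. At r = 0.7:
- k = 0.7: 1 + 0.49 − 0.98 = 0.51, equal to ANCOVA, so the loss is 0%.
- k = 1: 0.60, a loss of 8%.
- k = 1.5: 1 + 2.25 − 2.10 = 1.15, and √(1.15/0.51) − 1 = 50%.

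**At the planned effect.** With d = 0.70 and one later value, two-sided power by noncentral t for r = 0.3 / 0.5 / 0.7 / 0.8 is 79 / 91 / 99 / 99.9% for the change-score t-test and 93 / 97 / 99.6 / 99.98% for ANCOVA. The post-value t-test has 90.7% throughout. Except at low correlation, the gain at that effect is mainly a narrower interval. The undefined contrast matters too: at r = 0.3, choosing change scores over post values alone moves power from 91% to 79%.

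**The case against.** **Wilks' Lambda may be the main test.** It is listed first, it is tagged for repeated measures, and it alone handles all six times jointly; the t-tests may be follow-up comparisons. This stands as far as it goes, and the plan should not be described as comparing arms by t-tests only. But its role is not stated, and it gives no SpO2 difference or interval.

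**A reader might infer that Wilks' arm-by-time test cannot recover the lost precision. The documents do not support that.** The answer depends on the effect pattern, and neither the pattern nor the timing of measurements is given. Take a 0.35 SD effect (half the SAP's 0.70, an assumption), 45 per arm and all pairs of measurements equally correlated. Power for r = 0.3 / 0.5 / 0.7 / 0.8 is then:
- Steady shift at all five later times: Wilks 23 / 31 / 51 / 72%, ANCOVA on the five-value mean 79 / 79 / 88 / 96%.
- Effect at only two of the five: Wilks 36 / 49 / 75 / 91%, ANCOVA on that mean 20 / 20 / 24 / 31%.

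The ranking reverses. With one 30-minute session a day over two days (protocol section 10), a transient effect is arguable. Defining the contrast therefore comes before choosing the covariate.

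**The size is all assumption.** True. The range is wide and includes zero for change scores.

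**The t-test is valid and the change comes late.** Under intact randomisation an unadjusted t-test is not biased by lack of adjustment, so this is a point about precision. The study period closed in 2021 ("End Date: August 30, 2021") and SAP version 1.0 has "Date Last Updated/Approved: 26 May 2025", so adjustment added now is post hoc and must be labelled so.

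**Loss of precision may not be the only difference.** SAP sections 8 and 9 keep only patients who completed all six measurements. If that unbalances the first value between arms, change-score and ANCOVA estimates may differ in value as well as in width. A reader should not infer that adjustment cures this exclusion; it does not.

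**Conclusion.** The point holds in a limited form. Three omissions are plain in both documents: no baseline covariate, no defined SpO2 contrast, no named primary test. The one listed route to a between-arm difference with an interval is an unadjusted independent t-test, and its interval will usually be wider than the same data allow. The excess in standard error, 24% to 5% on change scores or 5% to 67% on post values, rests on assumed correlations of 0.3 to 0.8, equal SDs and one later value. The documents do not allow a figure for this trial. It is worth correcting, because the remedy is cheap if a true baseline exists, but confidence in its size is only moderate.

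**What to change.** 1. Define the six time points and name one primary SpO2 contrast.
2. Check that the first measurement precedes any prone session and has a counterpart in controls. The word change and the paired tests imply this, but the documents do not show it.
3. If so, estimate the between-arm difference for that contrast by ANCOVA, or by a repeated-measures model of the later values with arm, time and arm by time, adjusted for the first measurement. Treat the secondary outcomes in the same way.
4. Report the adjusted difference with its 95% CI alongside the listed tests, and say whether Wilks' Lambda tests arm by time.
5. State that the adjustment was specified after data collection, and deal with the completers-only exclusion separately.

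The cost is SAP wording, one degree of freedom, a post hoc label and a different procedure in the same software. No new data are needed if step 2 is met.
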